6.7.2. Pharmacokinetics (PK)

No blood samples will be collected for PK. If necessary, to establish correct dosing of an individual patient at a particular time, an aliquot of blood sample relevant to the suspect dosing from either the (6.7.3) surrogate marker (6.7.4) blood samples obtained from the patient.

6.7.3. Surrogate Markers

Blood samples will be collected for the surrogate marker measurements which shall include relevant inflammatory and immune markers, e.g., CD40/CD40L. Note: these samples must be collected from the arm not used for drug infusion. A total of17 blood samples will be collected for surrogate marker measurements: Pre-initial infusion of TK-112690 or placebo, at 5 and 24 hours and 48 hours post each initial infusion of TK-112690 or placebo as well as on Day 1 of Week 6. The blood samples will be collected in a 10 mL heparinized Vacutainers.

6.7.4. Blood Samples

A blood sample for CBC, Kidney function test, Liver Function test determination will be obtained 24 hours or so before each MTX dose to assure the patient is suitable for treatment with this chemotherapeutic. The sample will be processed at the local laboratory associated with the clinical site, and the data provided to the PI, the CRO and Tosk.

6.7.5 Summary of Blood Samples to be obtained.

A summary of the blood samples to be obtained in the study is provided in **Table 11**.

Table 11. Nature and total volume of blood samples

Purpose	Size (mL)	Time	Total Volume (mL) / Patient
CBC, Kidney function test, Liver Function test	7	Pre-dose Weeks 1-4	28

Laboratory Test	14	Screening Day 0 Weeks 1-4 (24 and 48 hours) Week 6	154
Surrogate Markers	5	Weeks 1-4 (pre-dose, 5, 24 and 48 hours) Week 6	85
	•	Total	267

6.7.6 Processing Blood Samples.

Blood sample each will be collected per **Table 11** above and Schedule of Events (**Table 12**) for Laboratory, Surrogate Marker measurements in a heparinized tube and immediately placed on ice. Within 30 minutes of collection, plasma will be isolated by centrifugation at $4^{\circ}C/1000*g$ for 10 minutes.

- CBC, Kidney function test, Liver Function test (7 mL): This is a test prior to dosing to demonstrate that the patient can safely be treated with methotrexate. The test will be performed at the laboratory used by the clinical site.
- Laboratory Test samples (14 mL): The plasma for the laboratory tests will be split into two equal parts, transferred into polypropylene freezer vials and then frozen at -20°C to -70°C. One of the two vials will be used for the Laboratory Tests performed at the site and the other vial will be sent to the central laboratory.
- Surrogate Marker samples (5mL). The plasma for sample) will be transferred to a polypropylene freezer vial and then frozen at -20°C to -70°C.

Specific shipping instructions will be issued by the analytical laboratory performing the analyses. The heparinized tube and freezer vial will be labeled with study code, subject number, subject initials, date and sampling time points. The plasma samples will be stored at the center until the study coordinator arranges transport to the analytical sites.

Laboratory test will be performed both at the central laboratory except . Assays used to measure surrogate markers will be performed at Tosk, or a CRO engaged by Tosk.

6.6 MUCOSITIS ASSESSMENT

Mucositis status in subjects will be assessed using scoring systems described in more detail in **Appendix 20.6**.

7.0. STUDY ACTIVITIES

Study visits should occur on the indicated visit day.

7.1. SCHEDULE OF EVENTS

Schedule of events are provided in **Table 12 below**. **Table 12.** Schedule of events (weekly cycle for 4 weeks and follow up at 6 week)

Englishting	Samooning	D. 0	Weeks 1, 2, 3, and 4					Week 6
Evaluation	Screening	Day 0	0h	5h	6h	24h	48h	Follow-up

Informed Consent ¹	Х							
I/E Criteria	Х							
Medical history ²	Х							
Test for drugs of abuse	Х	Х						
Physical examination ^{3,4}	Х	Х				X ⁵	X ⁵	Х
Vital signs and weight	Х	Х				X^6	X ⁶	X^6
ECOG	Х	Х						Х
Pregnancy test (females)	Х	Х						Х
12-Lead ECG	Х					Х		
Laboratory tests ⁷	Х	Х				Х	Х	Х
Randomization		Х						
CBC, Kidney function test, Liver Function test		X^8						
Nutritional supplement			X ⁹					
TK-112690/placebo treatments ¹⁰			X^{10}		X ¹³			
MTX treatment			X ¹¹					
Surrogate marker sample			X ¹²	Х		Х	Х	Х
Mucositis evaluation ¹⁴		Х				Х	Х	Х
Disease Status	Х							Х
AEs assessment				Х		Х	Х	Х
1 To be obtained before any	study-related	activities at	e perform	-d				

¹ To be obtained before any study-related activities are performed.

² Include a review of previous/ongoing medications for 180 days prior to enrollment.

³ Complete examination, including assessments of the skin, head, eyes, ears, nose, throat, neck, thyroid, lungs,

heart, abdomen, lymph nodes, extremities, and body weight.

⁴ Height will be measured at screening only.

⁵ Partial examinations to update findings from the examination performed at screening.

⁶ Include blood pressure, pulse, respiratory rate and temperature.

⁷ Includes serum chemistry, hematology (including coagulation), urinalysis; Hepatitis B/C & HIV only at screening

⁸ CBC, Kidney function test, Liver Function test at clinical site can be performed anytime within 24 hours of a methotrexate treatment (NEEDED FOR ALL MTX TREATMENTS, EG, TREATMENTS ON WEEKS 1, 2, 3, AND 4, TO VERIFY OK TO DOSE MTX)

⁹One hour before TK infusion/placebo

¹⁰ Beginning of TK-112690/placebo infusions is 0 hours. Dose is 45 mg/kg.

^{11 45} mg/m² one hour after TK-112690/placebo infusion.

¹² Pre-dose control samples for surrogate marker measurements.

¹³6 hours after TK-112690/placebo treatment, ie, 5 hours post MTX treatment

¹⁴See Section 20.6 for mucositis assessment scales.

7.1.1 Screening Visit

To be accomplished within 15 days of expected initial dosing and ONLY AFTER THE ICF IS SIGNED.

An Eligibility Screening Form (ESF) documenting the subject's fulfillment of the entry criteria for all subjects considered for the study is to be completed by the PI. Subjects who are considered for study entry, but who fail to meet the eligibility requirements, will also have an ESF completed with the reason for ineligibility. These subjects will not be entered into the trial database. The ESFs for subjects who fail to meet the eligibility criteria requirements should be kept in the files at the sites.

During this visit the following activities will be performed:

- Eligible subjects meeting the inclusion/exclusion criteria for this study will be asked to read, comprehend, and sign/thumb impression an informed consent form.
- The subject medical history and concomitant medication use will be recorded as well as a history of drug abuse, alcohol consumption, and tobacco use.
- Perform a urine screen for drugs of abuse.
- A complete physical examination will be performed assessing the following: Skin, eyes, ear, nose, throat, neck, thyroid, lungs, heart, abdomen, lymph nodes, extremities, and body weight.
- Vital signs and weight will be measured as well as an AE assessment.
- ECOG performance status (Section 20.2 Appendix 2)
- A pregnancy test will be performed on women of childbearing potential.
- A 12-lead ECG will be performed.
- The following laboratory test will be performed: hematological panel, infective agent panel, serum chemistry, coagulation and urinalysis (Laboratory tests, see **Table 10** for complete list of tests).
- Disease (tumor) assessment by CT scanning will be performed within 7 days post screening but before the first dosing.

7.1.2 Day before start of study (Day 0)

Prior to study start, all subjects will undergo the following:

- Randomization
- Perform urine screen for drugs of abuse.
- A physical examination to update findings from the examination performed at screening.
- Perform vital sign and weight measurements.
- ECOG performance status.
- A pregnancy test will be performed on women of childbearing potential.
- Perform laboratory tests (hematology, chemistry, coagulation and urinalysis).
- Perform a mucositis assessment (Section 20.6, Appendix 6).

7.1.3. Days 1 and 2 (Weeks 1-4)

Patients will be hospitalized on Day 1 and observed until after the 25-hour evaluations and plasma sample collection are obtained. All subjects will undergo the following on Days 1 and 2 of Weeks 1-4:

- An in-house CBC, Kidney function test, Liver Function test to be performed within 24 hours of expected methotrexate dosing to verify patient Fit to receive methotrexate.
- The nutritional supplement is ingested 2 hours prior to initiation of the MTX treatment, one hour prior to the TK-112690/placebo infusion.
- TK-112690/placebo is administered as a one hour infusion pre-MTX and 5 hours post-MTX (±15mins window period).
- One hour after the initial infusion of TK-112690 or placebo, MTX will be administered by continuous infusion for one hour (±15mins window period).
- Physical examination, vital signs, weight, mucositis evaluation at 24 and 48 hours post the initialTK-112690/placebo infusion.
- 12-lead ECG at 24 hours post initial TK-112690/placebo infusion.
- Laboratory tests (hematology, chemistry, coagulation and urinalysis) 24 and 48 hours post initial TK-112690/placebo infusion.

- Plasma samples will be collected for surrogate marker measurements pre-dose of the nutraceutical and 5, 24 and 48 hours initial infusion of TK-112690 orplacebo.
- Mucositis assessments (Section 20.6, Appendix 6) at 24 and 48 hours post initial infusion TK-112690 or placebo.
- AEs to be recorded at 5, 24 and 48 hours post initial infusion of TK-112690 or placebo.
- ± 15 mins of window period is considered acceptable for schedule of events.

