1.5.1.9 EKGs

12-Lead EKGs were obtained at screening and at 4, 12, and 24 hours post-dose. No drug-induced changes were noted.

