1.5.2.11 TK-112690 Pharmacokinetics (PK)

Blood samples for PK were obtained on each patient at Pre-dose (Day 1), 5 hours (Day 1), and 24 hour (Day1) post-dose, and TK-112690 measured by LC/MSMS in the harvested plasma. Reports on the PK⁸⁶ and LC/MS/MS assay⁸⁷ are available. Except for a few scattered measurements, TK-112690 concentrations in pre-dose samples were nm. The two following **Figures** provide the mean TK-112690 concentration data observed with dose and dosing interval.

Figure 12. Bar chart showing mean concentration of TK-112690, pg/mL ± SE, for individual dosing intervals at 5 hours post 15, 30, 45 or 60 mg/kg dose of TK-112690. Analysis includes data from all patients who completed 4 doses.Interval 1=Study Week 1, Interval 2=Study Week 2, Interval 3=Study Week 3, and Interval 4=Study Week 4.

[figure not shown]
[figure not shown]

Figure 13.Bar chart showing mean concentration of TK-112690, pg/mL ± SE, for individual dosing intervals at 24 hours post 15, 30, 45 or 60 mg/kg dose of TK-112690.Analysis includesdata from all patients who completed 4 doses.Interval 1=Study Week 1, Interval 2=Study Week 2, Interval 3=Study Week 3, and Interval 4=Study Week 4.

⁸⁶ Tosk FSR-CL-2690 0015: PK/PD of TK-11290 Administrated to Cancer Patients in Clinical Study CLP-2690-0002.

⁸⁷ Tosk FSR-CL-2690-0014: Method Validation for "Determination of TK-112690 in Human Plasma by LC/MS/MS"

The TK-112690 blood level data suggests:

- Plasma concentrations increase with increasing dose.
- The increase in concentration observed with the 60 mg/kg dose is somewhat less than expected.
- Comparing the 5-hour and 24-hour data, the terminal elimination half-life appears to be somewhat longer than the approximately 4 hours observed in the Phase 1a study. The estimated terminal elimination half-life in this study is approximately 6 hours.

[figure not shown]

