2.2. SECONDARY OBJECTIVES

The secondary objective of this study is to confirm the safety and tolerability of a continuous iv infusion of TK-112690 demonstrated in the Phase 1b study in patients suffering from local, advanced, residual recurrent, metastatic SCCHN receiving sequential continuous iv infusions of TK-112690 and MTX.

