6.5. VITAL SIGNS, WEIGHT DETERMINATIONS AND CARDIOVASCULAR ASSESSMENTS

Body temperature will be recorded by the oral, rectal or tympanic route at screening and during weekly visits. The same route should be used for all measurements, if possiblesupine blood pressure (systolic and diastolic), respiratory rate and pulse will be recorded at screening (defined as baseline) and at Day 0, and 24 and 48 hours post TK-112690 /placebo infusions as well as on Day 1 of Week6. The time of the measurements will be noted. All measurements will be made with the subject in the supine position. Blood pressure should be determined by cuff (manual or automated is acceptable, although the same method should be used throughout the study).

Weight will be determined concurrent with vital sign measurements.

A standard 12 lead ECG will be recorded at screening (defined as baseline) and at 24 post each TK-112690/placebo dosing. The PI will provide an overall judgment of the ECG.

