9.4.1. Precautions

Infusion reactions with the first dose of TK-112690 may be observed. TK-112690 administration should be interrupted in all subjects with severe infusion reactions and appropriate medical therapy administered.

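### The only scheduled on-treatment ECG (24 h) and vital signs (24 h and 48 h) come 17 h or more after the second infusion ends, at about 4-14% of peak drug level or less, so brief symptomless effects would largely be missed in the comparison with placebo

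*Combined protocol and SAP*

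**What the plan says.** The synopsis, section 6.5, section 7.1.3 and Table 12 give the same schedule in substance.

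- **ECG.** Section 7.1.3 has "12-lead ECG at 24 hours post initial TK-112690/placebo infusion". Section 6.5 has "A standard 12 lead ECG will be recorded at screening (defined as baseline) and at 24 post each TK-112690/placebo dosing", which drops the time unit and does not say which of the day's two infusions it means; the synopsis and 7.1.3 make clear that it is the first. There is no other ECG on treatment.
- **Vital signs.** Section 7.1.3 has "Physical examination, vital signs, weight, mucositis evaluation at 24 and 48 hours post the initialTK-112690/placebo infusion". Otherwise they are taken at screening, Day 0 and Week 6.
- **Clock.** Table 12, footnote 10: "Beginning of TK-112690/placebo infusions is 0 hours". The table puts the second infusion at 6 h. Each infusion lasts one hour.
- **Other safety observation.** Adverse events are recorded at 5, 24 and 48 h, and patients stay in hospital for about 25 h. Appendix 4 covers infusion reactions and includes recording of vital signs.
- **Purpose.** Section 2.2 sets out "to confirm the safety and tolerability of a continuous iv infusion of TK-112690". Section 10.3 summarizes vital signs by treatment group, and section 9.2.1 says that ECG abnormalities will be analyzed.

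**The concern.** Of the studies the protocol describes, this is the first in patients to set TK-112690 against placebo on the same MTX background. It can therefore separate a drug effect on ECG or vital signs from an effect of MTX or of the disease. It can do so only if the readings are taken while there is an appreciable drug level.

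No ECG or vital-signs reading is scheduled near the end of either infusion, when concentration is highest. If the drug briefly changed blood pressure, pulse or an ECG interval in step with its plasma level and caused no symptoms, both arms would probably look alike at 24 h. The report could then say that no effect was seen when this kind of effect had scarcely been looked for. Section 9.4.1 itself warns that "Infusion reactions with the first dose of TK-112690 may be observed", so events around the infusion are not a remote idea.

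**Working it through.** **Inputs**

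- Second infusion from 6 to 7 h (Table 12; one-hour duration). ECG at 24 h, that is 24 − 7 = 17 h after its end; last vital signs at 48 h, that is 41 h after.
- Half-life in Phase 1a: 3.92 h (Table 5). The same table's elimination constant of 0.19/h gives ln 2/0.19 = 3.65 h.
- Half-life in Phase 1b patients: "The estimated terminal elimination half-life in this study is approximately 6 hours".
- Phase 1a, 45 mg/kg over 4 h (Table 4): 79.60 µg/mL at 4 h, the end of infusion.

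**Step 1: reproduce the stated half-life.** Log-linear regression of the Table 4 means at 6, 8, 12 and 24 h gives 3.06, 5.07, 3.58 and 4.03 h at 15, 25, 35 and 45 mg/kg. The mean is 15.74/4 = 3.94 h, against 3.92 h stated.

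**Step 2: fraction of peak at each time.** Assume one compartment, first-order elimination and two equal one-hour infusions at 0 and 6 h, with k = ln 2/half-life. The peak is at 7 h. After that both infusions decay together, so the fraction left is 2^(−time since 7 h/half-life). Before it, the 1 h level is 1/(1 + e^(−6k)) of the peak and the 5 h level is e^(−4k)/(1 + e^(−6k)).

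| Time | Half-life 3.65 h | Half-life 6 h |
|---|---|---|
| 1 h, end of first infusion | 76% | 67% |
| 5 h, adverse event check | 35% | 42% |
| 7 h, end of second infusion | 100% | 100% |
| 24 h, ECG and vital signs | 2^(−17/3.65) = 4.0% | 2^(−17/6) = 14.0% |
| 48 h, vital signs | 2^(−41/3.65) = 0.04% | 2^(−41/6) = 0.9% |

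At 3.92 h the 24 h figure is 4.9%, and at 5 h it is 9.5%.

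**Step 3: sensitivity to the clock.** Suppose MTX starts an hour after the first infusion ends, and the five-hour gap runs from the end of MTX. The second infusion then starts at 8 h. The 24 h figures become 2^(−15/3.65) = 5.8% and 2^(−15/6) = 17.7%, and the 48 h figure is at most 2^(−39/6) = 1.1%.

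**Step 4: does Phase 1a already cover the peak?** "12-Lead EKGs were obtained at screening and at 4, 12, and 24 hours post-dose", and vital signs were also taken from 4 h, so that study did measure at the end of infusion. But the same dose over one hour gives a higher peak than over four, by 4(1 − e^(−k))/(1 − e^(−4k)). This is 1.18 at a 6 h half-life, 1.28 at 3.92 h and 1.30 at 3.65 h. The second infusion then multiplies the peak by 1 + e^(−6k), which is 1.50 at 6 h and 1.32 at 3.65 h. Scaling Table 4 gives a modelled peak of 79.60 × 1.18 × 1.50 = 141 µg/mL or 79.60 × 1.30 × 1.32 = 137 µg/mL.

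The text of section 1.5.1.10 puts the peak near 50 µg/mL at 35 or 45 mg/kg, where Table 4 has 58.69 and 79.60. The percentages in Step 2 depend only on half-life and are unaffected.

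**The case against.** The best case for the plan is that the risk is already low and partly watched.

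- Phase 1a saw no ECG or vital-sign change at the end of infusion.
- Telemetered monkeys given 100 mg/kg showed no ECG effect (Table 3). Table 2 lists a maximum of 220 µg/mL at that dose, above the 137 to 141 modelled here.
- Phase 1b gave this one-hour, twice-daily regimen with the same MTX dose, up to 60 mg/kg, with ECGs at unspecified times after dosing.
- Patients are under observation for about 25 h, with an adverse event check at 5 h and an infusion-reaction procedure.
- This is an exploratory pilot with a mucositis primary objective.

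All of this lowers the prior concern. None of it supplies a placebo-controlled reading near peak. Phase 1a was a single slower infusion in healthy men. Phase 1b had no placebo arm. Its Table 9 mentions vital signs at 4, 6 and 8 h, but the Week 1 counts (6, 6, 8 and 30 readings from 3, 3, 4 and 15 patients) are two per patient, which fits 24 and 48 h. Parts of the Phase 1b summary were not available to me, so I do not claim that no ECG was ever taken at the end of an infusion on this regimen.

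A reader might infer from the schedule that exposure-related effects cannot be seen at all. The documents do not support that. Symptomatic events can surface at 5 h, when the modelled level is 35 to 42% of peak. Treated reactions are recorded, and delayed or lasting effects would still show at 24 h.

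A reader might also take the residual straight from Table 4, 1.17/79.60 = 1.5%. That comes from one 4-hour infusion and understates the level here, because the second infusion ends later.

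**Conclusion.** The point holds for one class of effect: transient, concentration-related changes in ECG, blood pressure or heart rate that cause no symptoms. For these, the scheduled readings fall at about 4 to 14% of peak at 24 h (up to about 18% on the latest reading of the clock) and about 1% or less at 48 h. An absence of difference between arms would be weak evidence about them.

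The size rests on one-compartment kinetics and on the half-lives the documents report. A faster early decline, such as Table 4 shows between 4 and 6 h, would make the residual share smaller.

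The primary efficacy comparison is not affected, and the documents do not show that patients go unobserved around the infusions. This is a cheap improvement to the safety comparison and does not threaten the trial.

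**What to change.** In the synopsis, section 6.5, section 7.1.3 and Table 12, move the weekly ECG from 24 h to the end of the second infusion (about 7 h). Add one blood pressure, pulse and respiration set at that time in both arms. Keep the 24 h and 48 h vital signs. Tie the new time to the end of the infusion, not to a clock hour, and correct the wording in 6.5 in the same edit.

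The end of the second infusion is preferable to 1 h. It is the regimen's peak, where 1 h is 67 to 76% of it, and it comes after MTX, so a combined effect can also show.

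**Cost.** The number of ECGs stays at four per patient on treatment. One short vital-signs set is added per dosing day: 4 × 22 = 88 readings over the trial, in patients who are already in hospital. The 24 h ECG is lost. If the sponsor wants to keep it, an additional end-of-infusion ECG in Week 1 alone would cost 22 recordings.

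**Limit.** The baseline ECG remains the screening one, taken up to 15 days earlier, and there are 11 patients per arm. The retimed ECG would therefore show only large changes.
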